### 18.3 ADDITIONAL APPENDICES

### 18.3.1 INFORMED CONSENT FORM

### 18.3.2 KANSAS CITY CARDIOMYOPATHY QUESTIONNAIRE

### 18.3.3 NYHA QUESTIONNAIRE

### 18.3.4 PHQ-9 QUESTIONNAIRE

### 18.3.5 PATIENT SATISFACTION SURVEY

1 LIST OF ABBREVIATIONS

ACC	American College of Cardiology
AE	Adverse Event
AHA	American Heart Association
CI	Confidence Interval
CR	Cardiac Rehabilitation
CRT	Cardiac Resynchronization Therapy
CRT-D	Cardiac Resynchronization Therapy Device
DCRI	Duke Clinical Research Institute
DUHS	Duke University Health System
EMR	Electronic Medical Record
FDA	Food and Drug Administration
GCP	Good Clinical Practice
HF	Heart Failure
HIPAA	Health Insurance Portability and Accountability Act
ICD	Implantable cardioverter-defibrillator
ICF	Informed Consent Form
ICH	International Council for Harmonisation
IRB	Institutional Review Board
ITT	Intention To Treat
KCCQ	Kansas City Cardiomyopathy Questionnaire
MLM	Multilevel Modeling
NESTcc	National Evaluation System for health Technology Coordinating Center
NIH	National Institutes of Health
NYHA	New York Heart Association
PA	Physical Activity
PHI	Protected Health Information
PHQ-9	Patient Health Questionnaire 9
PI	Principal Investigator
PP	Per Protocol
PRO	Patient-Reported Outcome
QC	Quality Control
QOL	Quality of Life
SA	Safety Analysis
SAP	Statistical Analysis Plan
SD	Standard Deviation
US	United States

2 INTRODUCTION

The purpose of this statistical analysis plan (SAP) is to give a brief overview of the study design and study objectives, outline the types of analyses and presentations of data relevant to the study objectives, and provide a detailed description of the method in which the statistical analyses will be conducted to meet protocol objectives.

The analyses described in this SAP as well as the production of tables and listings will be performed using Version 9.4 or newer of SAS® (Cary, North Carolina) on Linux operating system. Additional statistical software may be used as needed.

3 STUDY OBJECTIVES

3.1 Primary Objective(s)

Compare the effects of remote cardiac rehabilitation (CR) on daily device measured physical activity (PA) over 12 weeks versus usual management.

- *Primary Outcome Measure:* Trajectory of the median Abbott ICD and CRT-D device measured daily PA obtained over the 1 month before randomization (baseline) and week 4, week 8, and week 12 after randomization among patients randomized to remote CR versus usual management.

3.2 Secondary Objectives

- 3.2.1 Secondary Objective #1 Compare the effect of remote cardiac rehabilitation on baseline and 12 week Kansas City Cardiomyopathy Questionnaire (KCCQ) HF symptom severity scores versus usual management.
- *Outcome Measure:* Change in Kansas City Cardiomyopathy Questionnaire (KCCQ) HF symptom severity scores from the baseline to the 12 week
- 3.2.2 Secondary Objective #2 Report Adverse Events of the remote cardiac rehabilitation during the intervention period
 - *Outcome Measure:* Adverse Events: heart failure hospitalization, fracture, myocardial infarction, serious adverse arrhythmia, and ICD therapy
- 3.2.3 Secondary Objective #3 Association between daily PA measured by the Abbott ICD or CRT-D device and in KCCQ HF symptoms severity score measured between baseline and end of follow up.
 - *Outcome Measure:* Change in daily PA measured by the Abbott ICD or CRT-D device between baseline and week 12 of treatment period and change in KCCQ HF symptoms severity score measured between baseline and end of follow up

4 STUDY DESIGN

4.1 Overall Design

This pilot study will be a single center randomized controlled trial involving 13 medically stable outpatients with HF, reduced ejection fraction, and previously implanted ICD or CRT-D devices followed longitudinally on the Abbott Medical Merlin remote patient monitoring network. Patients will be randomized in a 1:1 fashion to usual care plus a remotely administered home based weekly prescription for aerobic exercise or usual care alone. Patients will be screened based on inclusion and exclusion criteria which are located in Section 5 of protocol.

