## PROTOCOL SYNOPSIS

Protocol Number:	6292-2020-R2TCB36
Protocol Date:	24JUN2022
Test-Case ID/Title:	R2B36 Efficacy and Safety of ICD Remote Monitored Exercise Testing to improve Heart Failure Outcomes: REMOTE HF-ACTION (Pilot Randomized Controlled Trial)
Investigator(s):	[name]; [name]
Study Description:	
This pilot study will be a single center randomized controlled trial involving 50 medically stable outpatients with HF, reduced ejection fraction, and previously implanted ICD or CRT-D devices followed longitudinally on the Abbott Medical Merlin remote patient monitoring network. Patients will be randomized in a 1:1 fashion to usual care plus a remotely administered home based weekly prescription for aerobic exercise (intervention) or usual care alone (control). Usual care will include regularly scheduled visits with the clinical heart failure care team and medical therapy as prescribed by that team. The exercise prescription will be created by an exercise physiologist after incorporating remotely collected data from a patient directed smartphone app assessing HF symptom severity, vital signs, weight, and blood sugar, implantable device measures of physical activity, heart rate, heart failure volume status and heart rhythm, and Garmin measures of physical activity. We aim to determine if a remotely administered exercise prescription results in increased device measured physical activity and improvement in HF symptoms over a 12 week follow up interval.

Summary and Objectives:	
Primary Objective: Compare the median Abbott ICD and CRT-D device measured daily PA obtained over the 1 month before randomization (baseline) and 12 weeks after randomization among patients randomized to remote cardiac rehabilitation (CR) versus usual management.
 
Secondary Objective(s): Compare baseline and 12 week Kansas City Cardiomyopathy Questionnaire (KCCQ) HF symptom severity scores among patients randomized to remote CR versus usual management.

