**Exclusion Criteria**

- Prior participation in CR within the last year
- Unwillingness to sign informed consent form
- Currently performing <40 or >240 minutes of device detected daily PA
- Lack of a smartphone or unwillingness to use an App or Garmin device
- Prior left ventricular assist device (LVAD) implantation or heart transplantation
- ICD tachyarrhythmia therapies programmed off
- Inherited arrhythmia condition with contraindication to exercise (eg Lamin A mutation or ARVC)
- No transmissions through Merlin.net in past 12 months

---

Endpoints:	
Aim 1: Compare the median Abbott ICD and CRT-D device measured daily PA obtained over the 1 month before randomization (baseline) and 12 weeks after randomization among patients randomized to remote CR versus usual management.
 
Aim 2: Compare baseline and 12 week Kansas City Cardiomyopathy Questionnaire (KCCQ) HF symptom severity scores among patients randomized to remote CR versus usual management.
 
Aim 3: (Safety) Report Adverse Events of heart failure hospitalization, fracture, myocardial infarction, serious adverse arrhythmia, and ICD therapy.
 
Aim 4: Measure the correlation between change in daily PA measured by the Abbott ICD or CRT-D device between baseline and end of follow up and change in KCCQ HF symptoms severity score measured between baseline and end of follow up.

Statistical Methods:	Multilevel Modeling (MLM), Wilcoxon rank-sum tests and Pearson's correlation will be used to compare outcomes across treatment assignment. The expected sample size will be 50 subjects.
Target Population:	We will enroll patients followed in the Duke Health System Abbott Medical Merlin remote monitoring dataset who have heart failure and prior implantation of an ICD or CRT-D device. Patients will be ≥18 years of age. No enrollment restrictions will be based on gender or race.
Description of Sites/Facilities:	This will be a single center study performed at Duke University Health System.

---

Description of Study Intervention:	The study intervention will be a patient directed exercise prescription based on device measured physical activity and provided by a smart phone application.
Study Duration:	11 months
Participant Data Duration:	12/30/2020 to 11/15/2021
Additional Data Captured:	N/A

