## 5.6 STRATEGIES FOR RECRUITMENT AND RETENTION

Eligible patients will be identified by screening the Duke Epic EMR record of all patients currently followed longitudinally in the Duke/Abbott Merlin remote monitoring network. This network of real-world data, maintained by Abbott medical is used by health systems around the world for management of remotely collected data from patients with pacemaker, ICD, or CRT-D devices manufactured by Abbott medical. While the network contains data from patients with prior implantation of devices across the world, only patients actively followed at Duke will be included in this study. Patients will be enrolled without regard to their sex, race, ethnicity, or socioeconomic status.

We anticipate screening up to 500 subjects to identify 50 eligible subjects who are willing to participate. Subjects will be recruited by an invitation letter sent to them by Duke MyChart EMR message, physical mail, and follow up phone call in accordance to the recruitment plan provided by Duke Health Recruitment Innovations and approved by the Duke IRB.

We anticipate completing enrollment of the 50 subjects within 1 month of opening enrollment.

To maximize participant retention, the study team will keep the participant engaged through messages via the Pattern Health App, in combination with text messages and phone calls.

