4.2 Sample Size and Power

Sample size was determined based on the following power calculations:

For aim 1, a sample size of 28 subjects with 1:1 randomization each measured at 4 time points provides 81.1% power to detect a 15 minute per day difference in PA between groups at week 12 with a standard deviation of 19 minutes per day within each group and a within subject correlation of 0.7. A test based on a mixed-model analysis is anticipated at a significance level of 0.05.

For aim 2, a sample size of 50 subjects with 1:1 randomization provides 80.2% power to detect an 8% difference in KCCQ score between groups with a standard deviation of 10 in KCCQ score within each group and an alpha of 0.05.

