5 MODIFICATIONS

5.1 Modifications to the Approved Clinical Study Protocol

There are no modifications from the clinical study protocol (Version 8, dated June, 24 2022) that impact statistical analysis.

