5.2 Modifications to the Approved Statistical Analysis Plan

This is the first version of the SAP for the analysis.

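### SAP 4.1 describes a 13-patient trial, while the SAP's power figures are for 28 and 50 and the protocol plans 50; the 13 is unexplained, and if it stands power is well below 80%

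*SAP*

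**What the plan says.** Three sample sizes appear in the two documents.

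- **13.** SAP 4.1 (Overall Design) describes a "single center randomized controlled trial involving 13 medically stable outpatients with HF". The sentence otherwise follows the protocol's study-design sentence closely, with 13 where the protocol has 50.
- **28 and 50, as the basis for power.** SAP 4.2 says that for aim 1 "a sample size of 28 subjects with 1:1 randomization each measured at 4 time points provides 81.1% power" to detect a 15 min/day difference in PA at week 12, with SD 19 and within-subject correlation 0.7. For aim 2, "a sample size of 50 subjects with 1:1 randomization provides 80.2% power" to detect an 8% KCCQ difference with SD 10. Protocol 11.4 has the same two calculations.
- **50, as the plan.** The Protocol Synopsis describes a "single center randomized controlled trial involving 50 medically stable outpatients with HF". Its Statistical Methods entry says "The expected sample size will be 50 subjects". Protocol 5.6 says "We anticipate screening up to 500 subjects to identify 50 eligible subjects who are willing to participate".

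SAP 5.1 says "There are no modifications from the clinical study protocol" (Version 8) that affect the statistical analysis. SAP 5.2 says "This is the first version of the SAP for the analysis". The protocol's amendment history records no change of sample size.

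**The concern.** A reader of the SAP cannot tell how large the trial is. Section 4.1 gives 13, the next numbered section at the same level derives the size from calculations for 28 and 50, and the protocol gives 50. The number 13 could be a revised target, the number actually enrolled, or a slip. Each reading calls for a different correction.

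The size matters because Protocol 11.3 makes study success depend on a statistically significant PA difference in the ITT population, and SAP 4.1.1 also rests success on ITT. Protocol 9.1 adds that the results will be used to design a pivotal trial. If 13 is the real size, a null PA result would be read against the only PA power on record, 81.1% at 28 patients. The SAP gives no power or precision for 13. In addition, the P1 reporting text in SAP 6.3 lists the slope difference and its p-value but no confidence interval, although Protocol 11.1.2 promises one for P1. With so few patients, the interval is what would show how little a null result rules out.

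**Working it through.** **Inputs.** From SAP 4.2: PA difference 15 min/day at week 12, SD 19, correlation 0.7, four time points; KCCQ difference 8 and SD 10. From SAP 6.1.1: two-sided alpha 0.05. From SAP 6.3: continuous time and a difference in slopes, with measurements at weeks 0, 4, 8 and 12. From SAP 4.3: 1:1 allocation.

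**Assumptions.** 13 patients split 6/7; compound symmetry; no dropout (SAP 4.2 gives none); the 8% KCCQ difference read as 8 points.

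**Formula for PA.** The sum of squared deviations of the four times is Sxx = 36 + 4 + 4 + 36 = 80. The per-patient SD of the slope, scaled to 12 weeks, is

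12 × 19 × √((1 − 0.7)/80) = 13.96 min/day.

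The standard error of the between-group difference is 13.96 × √(1/n₁ + 1/n₂). The normal approximation gives power = Φ(15/SE − 1.96). The t version uses the noncentral t with N − 2 df.

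**Reproducing the plan's figures first.**

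- PA at 14/14: SE = 5.28, 15/5.28 = 2.84, Φ(0.88) = 81.1%. This matches the stated figure. The t version gives 78.1%.
- KCCQ at 25/25: SE = 10 × √(2/25) = 2.83, 8/2.83 = 2.83, power 80.7% (normal) and 79.1% (t), either side of the stated 80.2%.

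The 8-point reading is the one that fits. If 8% were relative to an assumed baseline of 60–80 (4.8–6.4 points), power at 50 would be only about 38–62%.

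**Other sizes with the same inputs.**

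| | SE | Power, t | Power, normal |
|---|---|---|---|
| PA, 28 (14/14) | 5.28 | 78.1% | 81.1% |
| PA, 50 (25/25) | 3.95 | 96.1% | 96.7% |
| PA, 13 (6/7) | 7.77 | 42.2% | 48.9% |
| KCCQ, 50 (25/25) | 2.83 | 79.1% | 80.7% |
| KCCQ, 13 (6/7) | 5.56 | 26.0% | 30.1% |

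At 13 the chance of missing a true 15 min/day effect is 100 − 48.9 = 51% to 100 − 42.2 = 58%. A simulation of a slope t-test at 6/7 (40,000 runs) gave 42.4% power, in line with the t figure.

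**Precision at 13 (t, 11 df).** The difference detectable with 80% power is about 23.9 min/day or 17.1 KCCQ points, against the planned 15 and 8. The 95% CI half-width is 2.201 × 7.77 = 17.1 min/day for PA and 2.201 × 5.56 = about 12 points for KCCQ.

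**Sensitivity at 13.**

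- 5/8 split: PA 40.5–47.0%.
- 11 evaluable patients (5/6): PA about 35–43%, KCCQ about 22–26%.
- Extra between-patient slope SD over 12 weeks (assumed, because SAP 6.3 fits random slopes): PA 38.2–44.4% at 5 min/day and about 30–35% at 10 min/day.

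**The case against.** The strongest reply is that little here is truly contradictory. SAP 4.2 is written as design history: it explains how the size was set and claims no power for 13. The figures 28 and 50 do not conflict, since 50 covers both aims. SAP 5.1 denies only changes that affect the analysis; if 13 is an enrolment shortfall, the model, endpoint and populations are unchanged and the statement could be literally true. SAP 5.2 contradicts nothing by itself. Power recomputed after enrolment adds little to the observed confidence interval. The 42–49% range rests on compound symmetry and complete data, and it covers only the choice between t and normal. The missing interval in SAP 6.3 has its own origin: Protocol 11.8.1 omits it too. Finally, the study is called a pilot, and some SAP pages were not in the public text.

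Much of this is fair. The range is conditional and should carry its assumptions, and the confidence interval is a separate, smaller omission. The central mismatch remains. SAP 4.1 presents 13 as the design, in the future tense, beside power figures for other sizes and with no label. Nothing in the available text lets a reader choose between a shortfall, a new target and a slip. The pilot label is used to waive multiplicity control, but it does not remove the success criterion based on ITT significance.

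**Conclusion.** The concern holds, and the text must be corrected before the SAP is relied on. The sample size in SAP 4.1 is either wrong or unreconciled with SAP 4.2 and the protocol.

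The consequence depends on what 13 is. If it is an error and 50 stands, power is not overstated. If 13 is the real size, power falls to about 42–49% for PA and 26–30% for KCCQ under the assumptions stated above; dropout, uneven allocation or extra slope variance would lower it further. That power is well below 80% is secure; the exact range is not. The KCCQ figure bears only on aim 2, because KCCQ is not part of the success criterion.

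**What to change.** State in SAP 4.1 what 13 is, and reconcile SAP 4.1, 4.2 and 5.1 with the protocol.

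- **If 13 is an error:** correct SAP 4.1. The power figures in SAP 4.2 can stay.
- **If 13 stands:** label the figures for 28 and 50 in SAP 4.2 as the original design and add wording such as: *With 13 patients (6/7 split, SD 19, correlation 0.7, compound symmetry, no dropout; KCCQ 8% taken as 8 points, SD 10), power is about 42–49% for 15 min/day and 26–30% for 8 KCCQ points (t to normal approximation). On the t basis, 80% power needs about 24 min/day or 17 points, and expected 95% CI half-widths are about 17 min/day and 12 points.* Record the change from 50 in SAP 5.1 and say whether it is a change of plan or an enrolment shortfall. State with Protocol 11.3 that a non-significant PA result at this size is not evidence of no effect.
- **In either case:** add to the P1 reporting text in SAP 6.3 the 95% CI for the slope difference, as Protocol 11.1.2 already promises.

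The cost is wording in SAP 4.1, 4.2, 5.1 and 6.3 and, if 13 stands, one sentence with Protocol 11.3. No extra patients are asked for. If 13 stands, the stated power becomes less favourable.

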4.1.1 Analysis Population

Effectiveness will be assessed in the Intent-To-Treat (ITT) population and in the As-treated (AT) populations. Both analysis populations will be examined for all objectives, however, the success of the trial will be based on the analysis of the ITT population.

- Intent-to-Treat (ITT) Population: All participants who were randomized. Subjects will be analyzed according to the treatment group to which they were randomized, regardless of whether they received that intervention. This population will include participants who may have received the wrong intervention and have protocol violations.
- Safety Analysis (SA) Population: All participants who had at least one session on the study app.
- As-Treated (AT) Population: The treatment assignment of this population will be based on the actual treatment patients received, not the treatment the patients were randomized to receive.

Deviations related to treatment compliance with randomized intervention: Participants not meeting the adherence requirement of completing at least 2/3 of expected app check in sessions will be considered a protocol deviation and excluded from the AT analysis population.

Any additional exclusion of any subject from a data presentation, other than those described above and in the section on handling of missing data, will be considered on a case-by-case basis, and will be described in the final study report.

4.1.2 Study Periods

For each enrolled participant, the study will consist of 3 Periods as follows:

- Screening/Enrollment Period – screening/enrollment begins after IRB approval prior to Baseline.
- Baseline Period - the first month (Day -30 – Day -1) of the study prior to the treatment period.
- Treatment Period - Following the baseline period, patients will be randomized 1:1 to either remote CR or usual care through the CR app and will be followed up for 12 weeks (Day 1 – Day 84).

4.2 Sample Size and Power

Sample size was determined based on the following power calculations:

For aim 1, a sample size of 28 subjects with 1:1 randomization each measured at 4 time points provides 81.1% power to detect a 15 minute per day difference in PA between groups at week 12 with a standard deviation of 19 minutes per day within each group and a within subject correlation of 0.7. A test based on a mixed-model analysis is anticipated at a significance level of 0.05.

For aim 2, a sample size of 50 subjects with 1:1 randomization provides 80.2% power to detect an 8% difference in KCCQ score between groups with a standard deviation of 10 in KCCQ score within each group and an alpha of 0.05.

4.3 Randomization and Blinding

Treatment assignment will be randomized in a 1:1 fashion. Randomization will be performed in the Pattern Health App. Neither the patient nor the study team will be blinded to treatment assignment. Randomization will be stratified based on patient sex and non-ischemic versus ischemic cardiomyopathy etiology.

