6.3 Primary Endpoint Analyses

P1: Compare the trajectory of the median Abbott ICD and CRT-D device measured daily PA obtained over the 1 month before randomization (baseline) and week 4, week 8, and week 12 after randomization among patients randomized to remote CR versus usual management.

Analysis strategy for P1: The outcome variable for this objective is the median Abbott ICD and CRT-D device measured daily PA obtained over the 1 month before randomization (baseline) and week 4, week 8, and week 12 after randomization. This endpoint represents a summary measure. The hypothesis test will evaluate whether the trajectory of the mean Abbott ICD and CRT-D device measured in the remote CR treatment group is different from the trajectory in the usual management group. The test will be a multilevel modeling (aka mixed models) on trajectories of the outcomes over the study period. In the multilevel model, time (week of study), treatment group, and the interaction between treatment group and time will be handled as fixed effects. Time will be modeled as a continuous variable. The model will include random effects for subject-specific intercepts and slopes, with unstructured covariance for random intercepts and slopes.

Reporting for P1: Descriptive summaries of the median physical activity at baseline and 4 weeks, 8 weeks, and 12 weeks after randomization will be presented by treatment group. The estimated difference in slopes of trajectories from the CR and usual care treatment groups will be presented, along with the p-value for comparing the trajectories over the study period. If differences are noted with regard to baseline covariates adjusted analyses will be performed for the primary endpoint.

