6.4 Secondary Endpoint Analysis

S1: Compare the change in mean HF symptom severity scores at baseline and 12 week as measured by Kansas City Cardiomyopathy Questionnaire (KCCQ) among patients randomized to remote CR versus usual management.

Analysis Strategy for S1: The outcome variable for this objective is the mean change in HF symptom severity scores from 1 week before randomization (baseline) to 12 weeks, calculated as the HF symptom severity scores in week 12 minus the mean of baseline period. The hypothesis test will evaluate whether the mean change in the remote CR treatment group is different from the mean change in the usual management group. The test will be a two-sample t-test allowing for unequal variances.

Reporting for S1: Descriptive summaries of the mean physical activity at baseline and 12 weeks, as well as the 12-week change mean will be presented by treatment group. The summary statistics of the score at baseline, at 12-weeks and change from baseline will be reported for each treatment group. The mean difference (95% CI) between the CR and usual care treatment groups for change from baseline will be presented, along with the t-test p-value. If differences are noted with regard to baseline covariates adjusted analyses will be performed for the Secondary endpoint.

S2: (Safety) Report Adverse Events of heart failure hospitalization, fracture, myocardial infarction, serious adverse arrhythmia, and ICD therapy among randomized patients .

Reporting for S2: A listing of Adverse Events will be produced for the study population.

S3: Investigate the correlation between change in daily PA as measured by the Abbott ICD or CRT-D device between baseline and week 12 after randomization and change in HF symptoms severity scores as measured by KCCQ during same time period.

Analysis Strategy for S3: The variables used for this objective are the change in median PA from baseline to week 12, and the change in HF symptom severity score from baseline to week 12. The hypothesis test will evaluate whether there is a correlation between these two variables, pooling subjects across treatment groups..

Reporting for S3: We will be reporting the strength of the correlation and related p value and 95% CI.

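### S1 is tested without the two factors that stratify randomisation; if they predict KCCQ change, its interval is wider than needed and its test conservative

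*SAP*

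**What the plan says.** Protocol 4.3 and SAP 4.3 agree on the design. "Treatment assignment will be randomized in a 1:1 fashion", and then: "Randomization will be stratified based on patient sex and non-ischemic versus ischemic cardiomyopathy etiology". That gives four strata.

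Neither factor appears in the effectiveness analyses:

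- **P1 (SAP 6.3).** "In the multilevel model, time (week of study), treatment group, and the interaction between treatment group and time will be handled as fixed effects". Subject-level random intercepts and slopes are added, and the reported contrast is the difference in slopes between arms.
- **S1 (SAP 6.4).** The outcome is week-12 KCCQ symptom score minus baseline. "The test will be a two-sample t-test allowing for unequal variances".
- **Baseline-adjusted sensitivity analysis (SAP 6.7).** It applies to P1 and adds only the baseline mean.

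The one route to covariate adjustment is conditional. For P1: "If differences are noted with regard to baseline covariates adjusted analyses will be performed for the primary endpoint". SAP 6.4 has the same clause for S1, and Protocol 11.8.2 has it for the secondary endpoints. Protocol 3.2 says the opposite: secondary outcomes get no adjusted comparisons.

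**The concern.** Stratified randomisation balances the arms on sex and aetiology. That balance removes between-stratum variation from the true sampling error of the treatment difference. A t-test does not know this and leaves the variation in its standard error. To the extent that the factors predict the outcome, the interval is wider than the design warrants and the test rejects less often than its nominal level.

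The conditional clause does not close the gap. It has no threshold and no covariate list. It is read off baseline comparisons whose p-values will be on the table (SAP 6.2.2), in an unblinded trial. It is also least likely to pick up the two factors that the design has already balanced.

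At stake is the precision of S1, which Protocol 9.1 intends as an input to a larger pivotal trial.

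**Working it through.** **The plan's own figures (Protocol 11.4, SAP 4.2).**

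- *Aim 1:* 28 patients, 15 min/day, SD 19, correlation 0.7, four time points. With weeks 0, 4, 8 and 12, the sum of squared deviations of time is 80. The SD of 12 times a subject's slope is 12 × 19 × √((1 − 0.7)/80) = 13.96. With 14 per arm, the normal approximation gives 81.1%, exactly as stated.
- *Aim 2:* 50 patients, difference 8 (the stated 8% read as 8 points), SD 10. The SE is 10 × √(2/25) = 2.83. Power is 80.7% (normal) or 79.1% (noncentral t), against 80.2% stated.

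Neither calculation uses the strata.

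**S1: assumptions.** R2 is the share of the variance of KCCQ change explained by sex and aetiology together. It is set at 0 to 30%, split equally between the two factors. SD 10 is applied to the change score. The simulations use stratified permuted blocks (size 4, with 2 as a variant), 40% women (Protocol 5.1 expects 30-50%) and 50% ischaemic. Block size and the ischaemic share are not in the documents.

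**S1: formulas.**

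- Width ratio, adjusted/unadjusted = √(1 − R2) × t(N − 4)/t(N − 2), with t the 97.5% quantile.
- True level of the unadjusted test under exact balance = 2 × [1 − Φ(1.96/√(1 − R2))], which is 3.9%, 2.8% and 1.9% at R2 of 10%, 20% and 30%.

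Thirteen patients in four strata average about three each, so exact balance will not hold there. Simulated levels are therefore used below.

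| R2 | Width ratio, N=50 | Adjusted power, N=50 | True level of t-test, N=50 | Width ratio, N=13 | True level of t-test, N=13 |
|---|---|---|---|---|---|
| 0 | 1.00 | 79.1% | 4.7% | 1.03 | 4.4% |
| 10% | 0.95 | 83.1% | about 4.0% | 0.98 | 4.0-4.2% |
| 20% | 0.90 | 87.2% | 2.5-3.3% | 0.92 | 3.3-3.4% |
| 30% | 0.84 | 91.1% | 2.3-2.4% | 0.86 | 2.6-2.7% |

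The ranges span simulation settings and simulation error. The adjusted model held 4.6-5.0% at N=50.

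**Cost in degrees of freedom.**

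- N=13: t goes from 2.201 (11 df) to 2.262 (9 df), a ratio of 1.028, so the formula breaks even at R2 = 1 − 1/1.028² ≈ 5%. With baseline KCCQ as a third term, t(8) = 2.306 and the ratio is 1.048.
- N=50: 2.013/2.011 = 1.001.
- The formula leaves out residual imbalance. In simulation at N=13 (block size 4), the median width ratio was 1.05, 1.02 and 1.00 at R2 of 0, 5% and 10%. A typical small trial therefore breaks even nearer 10%.

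**P1.** A sex or aetiology main effect is constant over time and drops out of every subject's slope. In complete simulated data the arm-by-time estimate was identical with and without the main effects, and its SE was unchanged apart from optimiser noise. Only stratum-by-time terms can change it. In six simulated trials of 28 patients where strata did not affect slope, adding those terms raised the SE every time. The smallest rise was from 5.96 to 6.26 (5%) and the largest from 7.68 to 8.85 (15%).

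**The case against.** The strongest reply is that this is a matter of efficiency in a hypothesis-generating pilot. The error is conservative, no false claim is made more likely, and R2 is unknown. S1 is already a change score, so constant KCCQ differences between strata cancel; the factors must predict change. All of this stands. It limits the point to a refinement, but it does not explain why S1 should leave out the factors the design chose.

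Three stronger readings are tempting, and the documents support none of them:

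- *That P1 is harmed in the same way.* The P1 contrast is a difference in slopes, which main effects leave alone. Nothing in the documents suggests that sex or aetiology predicts the 12-week activity trend. Stratum-by-time terms would give a model with eight fixed effects and four variance parameters for, on SAP 4.1's count, 13 patients and at most 52 observations.
- *That precision already bought is being thrown away.* Neither power calculation counted on the strata, and both reproduce, exactly or closely, without them.
- *That the exact-balance error rates apply at N=13.* They overstate the conservatism there, as the table shows.

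A reader might also say that the conditional clause already provides for adjustment. It does so only where imbalance is noticed, and Protocol 3.2 forbids it for secondary outcomes altogether.

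**Conclusion.** The point holds for S1. Its planned test omits both stratification factors, and the conditional clause will rarely bring them in. The consequence is a conservative test and a wider interval, never an inflated error.

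The size depends wholly on an assumed R2. At N=50, an R2 of 10-30% makes the unadjusted interval about 5-20% wider than the adjusted one. Below an R2 of about 5% the difference is slight. At N=13 there is nothing to gain below about 5-10%.

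For P1 there is no case for changing the primary model. With missing weeks, main effects could have a small influence on the slope contrast, but not enough to alter that conclusion.

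**What to change.** 1. **SAP 6.4, S1:** make the primary analysis a linear model of KCCQ change on arm, sex and aetiology. Baseline KCCQ may be added. Keep the unequal-variance t-test as a sensitivity analysis, which also covers the linear model's common-variance assumption.
2. **Conditional clause for S1:** replace it in SAP 6.4 and Protocol 11.8.2 with this fixed rule.
3. **Protocol 3.2:** reconcile its bar on adjusted secondary analyses with Protocol 11.8.2 and SAP 6.4. The change therefore needs a protocol edit as well as a SAP edit.
4. **P1:** keep the SAP 6.3 model as primary, and state that stratum main effects do not change the slope contrast with complete data. Add a model with sex, aetiology and their time interactions only as a prespecified sensitivity analysis in SAP 6.7.

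The cost for S1 is two residual degrees of freedom, or three with baseline KCCQ. The critical t is about 3-5% larger at N=13 and negligibly larger at N=50. At N=13 the adjusted interval may be slightly wider if the factors turn out to explain little.
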